## 6.2 POST-DOSE VISIT (CLINIC VISIT 17; STUDY DAY 1099)

If the subject completes the study (or discontinues from the study early), and is not transitioning to another extension protocol or switching to commercially available drug, the subject will visit the clinic on Study Day 1099 (or 14 days after the day of discontinuation)

The following procedures will be performed:

- Record AEs
- Record AESI
- Record concomitant medications

- Collect used, partially used and unused study medication; perform drug accountability and review with parent/caregiver

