**Duration of Treatment:**

All subjects will receive ZX008 for up to approximately 36 months. All subjects, including those who prematurely discontinue from the study, will undergo an up to 2-week taper of study medication, at the conclusion of the study.

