- f: For subjects enrolling from one of the core studies, use core study Visit 12 information unless complete neurological examination is warranted based on significant changes in subject status.
- g: ECHOs will be performed at Months 1, 3, 6, 9, 12, 15, 18, 21, 24, 27, 30, and 33.
- h: The Months 3, 6, 9, 12, 15, 18, 21, 24, 27, 30, and 33 ECHO may be performed any time within 3 weeks prior to the study visit. If a subject discontinues early from the study, the ECHO should be scheduled as soon as practical (see Table 7).
- i: Females of child-bearing potential
- j: For subjects enrolling from one of the core studies, use data collected at Visit 12 of ZX008-1501 or ZX008-1502 for Visit 1 unless clinical laboratory evaluation is warranted based on significant changes in subject status. Visit 2 clinical laboratory evaluation is optional based on subject status for all cohorts.
- k: Visits 6, 15, and 27 only.
- l: Visits 3 and 4 (Months 1 and 2) only.
- m: Only adverse events related to cardiac safety will be collected at this visit (see Table 7).
- n: Not to be completed for de novo subjects >18 years old.
- o: For subjects who are entering the separate extension trial or who transition to commercially available drug, post-dosing and cardiac safety follow-up visits are not required in this trial.

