### **3.3 STUDY DURATION**

The duration of participation in the study for an individual subject is expected to be up to 158 weeks, plus follow-up safety visit 3 and 6 months after the last dose:

- OLE Treatment Period - 36 months (156 weeks)
- Post-Dosing Visit - 2 weeks after study completion or early termination
- Cardiac Follow-up (ECG and ECHO) - 3 and 6 months after study drug discontinuation for early termination and for those subjects who complete the study; not applicable to subjects who transition to commercial product.

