### 5.4.2.1 Taper Period for Subjects not Receiving Concomitant STP

The tapering scheme is a 2-step process for subjects who are not receiving concomitant STP, including subjects from core studies ZX008-1501 and ZX008-1502, and from study ZX008-1504 Cohort 1/Regimens 1&2. This is described in [Table 5](#).

Study medication will be administered as equal doses BID in the morning and in the evening, approximately 12 hours apart, with food. Each dose should be separated by a minimum of 8 hours and a maximum of 12 hours. A missed dose of study medication may be taken later up to 8 hours before the next scheduled dose; otherwise, the missed dose should not be given. IMP will be administered using the oral dosing syringe provided.

**Table 5. Taper Algorithm for Subjects from Core Studies ZX008-1501, ZX008-1502, and ZX008-1504 Cohort 1/Regimens 1&2 Not Receiving Concomitant STP**

Current Dose	Taper Step 1 Days 1-4 after study completion or early termination	Taper Step 2 Days 5-8 after study completion or early termination
ZX008 0.2 mg/kg/day	Not applicable	Not applicable
ZX008 0.4 mg/kg/day	ZX008 0.2 mg/kg/day	Not applicable
ZX008 0.6 mg/kg/day	ZX008 0.4 mg/kg/day	ZX008 0.2 mg/kg/day
ZX008 0.8 mg/kg/day	ZX008 0.4 mg/kg/day	ZX008 0.2 mg/kg/day

Note: maximum daily dose of ZX008 is 30 mg.

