**Table 7. Time Windows for Assessments**

Visit / Procedure	Time window (relative to scheduled visit / procedure)
Visit 1 (Clinic; Study Day 1)	Not applicable (this is the same visit as Visit 13 from the core study)
Visits 2 (Clinic/Phone; Study Day 15)	± 3 days
Visits 3-15 (Clinic; Study Days 30, 60, 90, 180, 270, 365, 455, 545, 635, 725, 815, 905, 995)	± 4 days
Visit 16 (Clinic; Study Day 1085)	± 4 days
Visit 17 (Clinic; Study Day 1099; post dosing)	± 4 days
Visit 18, 19 (ECHO clinic; 3 and 6 months after last dose)	+ 30 days
Blood collection for AED concentration	Prior to morning dose of AED medication

AED=antiepileptic drug (s); ECHO=echocardiogram

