### **6.1.5 Clinic Visit 16 (Month 36): End of Study/Early Termination**

The End-of-Study participation for an individual subject occurs after he/she has received IMP for 3 years in the OLE Treatment Period or if the subject is transitioning to receive ZX008 in a separate extension protocol when available or until ZX008 is approved in a subject's country of residence and listed on a patient's health plan formulary, whichever occurs first.. The End-of-Study visit may also occur if the subject withdraws participation from the study or the Sponsor terminates the study.

Subjects will visit the clinic for the End-of-Study visit if one the following events occur:

1. The subject withdraws or is withdrawn from participation in the study.
2. The Sponsor terminates the study.
3. The subject completes all study related visits and procedures.
4. The subject is being transitioned to another extension study or transitioning to commercially available drug.

The following procedures will be performed:

- Review current seizure activity (number/type/duration) from diary since previous visit
- Record concomitant medications
- Complete physical examination, including height and weight, and calculation of BMI
- Complete neurological examination
- Obtain vital signs
- 12-lead ECG
- Doppler ECHO (must be performed any time between Study Day 1064 and Study Day 1085; if subject terminates early from the study, the ECHO should be scheduled as soon as practical). If the Month 3, 6, 9, 12, 15, 18, 21, 24, 27, 30, or 33 ECHO was completed  $\leq$  30 days prior to early termination, the Visit 12 ECHO will not be performed provided the parent/guardian agrees to bring the subject to the clinic for the cardiac follow-up visit (Table 8).
- Urine pregnancy test for females of child-bearing potential

- Laboratory evaluation (serum chemistry and hematology, and urinalysis)
- Urine THC panel
- Whole blood CBD
- Collect plasma sample for AED PK evaluation prior to the morning dose of study medication(s)
- Tanner Staging for subjects > 7 to ≤18 years of age ([Appendix 5](#))
- Collect and review diary with parent/caregiver
- C-SSRS Children's Since Last Visit Assessment ([Appendix 2](#))
- CGI-I (assessed by parent/caregiver)
- CGI-I (assessed by investigator)
- BRIEF ([Appendix 3](#))
- QOLCE ([Appendix 4](#))
- PedsQL ([Appendix 6](#)) (only for subjects from the core studies)
- Parent/Caregiver QoL using the EQ-5D-5L scale ([Appendix 7](#))

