### 8.4 OBSERVATION PERIOD FOR ADVERSE EVENT REPORTING

The observation period for AE and SAE reporting for de novo subjects will start at the time of giving written informed consent for participation in the current study and finish 15 days after the last dose of study drug or the last visit, whichever is later. For subjects who participated in one of the core studies, the observation period for adverse events will start at Visit 1 of 1503 and finish 15 days after the last dose of study drug or the last visit, whichever is later. Ongoing AEs from the core studies will be considered medical history unless there is an increase in the frequency or severity of the condition from the core study.

If the investigator becomes aware of an SAE that has started after the observation period has finished, and the event could in some way be associated with IMP (irrespective of whether or not it is considered by the investigator to be causally related to IMP), then this must also be reported to the Sponsor (see Section 8.6).

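### The post-dose visit and the TEAE cut-off are timed from study completion, not from the last taper dose, so both fall 1, 5 or 9 days short of the 15 days after last dose in section 8.4

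*Protocol*

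**What the plan says.** **Visit timing.** Table 7 places the end-of-study visit at "Visit 16 (Clinic; Study Day 1085" and Visit 17 at Study Day 1099, each with a window of ±4 days. Section 6.2 states that "the subject will visit the clinic on Study Day 1099 (or 14 days after the day of discontinuation", and section 3.3 gives the same anchor: "Post-Dosing Visit - 2 weeks after study completion or early termination".

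**Taper.** Study medication is dispensed at Visit 16 to subjects who are not moving to another ZX008 source (6.1.5). Tables 5 and 6 count the taper from the same completion or termination point; the last step with a dose in either table is "Taper Step 2 Days 5-8 after study completion or early termination". The synopsis says that subjects "will undergo an up to 2-week taper of study medication, at the conclusion of the study".

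**AE windows.** Under section 8.4, AE and SAE observation will "finish 15 days after the last dose of study drug or the last visit, whichever is later". Section 10.5.1 counts an event as treatment emergent only if it begins by the end of the Post-dosing Period. Section 10.4 sets that period at two weeks, starting when the OLE Treatment Period ends.

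**Later contacts.** At Visits 18 and 19, three and six months after the last dose, Table 1 footnote m says: "Only adverse events related to cardiac safety will be collected at this visit". Table 2 footnote l is the same.

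**Diary.** Section 6.1.5 lists "Collect and review diary with parent/caregiver" at Visit 16 and no dispensing. Tables 1 and 2 show collect/review at both Visit 16 and Visit 17. Section 6.2 does not mention the diary.

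**The concern.** Three clocks that should agree use two different starting points. Section 8.4 and the cardiac follow-up visits count from the last dose. Visit 17 and the Post-dosing Period count from completion or discontinuation, when subjects on more than the lowest dose are still taking drug. Part of the two-week post-dose interval is therefore spent on taper doses, and the part spent off drug is shortest for subjects who stop from the highest doses.

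Long-term safety is the primary objective, and this interval is when withdrawal effects would appear. The protocol itself accepts (1.10) that some subjects may worsen on moving to a lower dose. An event late in the 8.4 window depends on spontaneous report, and if reported it is left out of the TEAE tables.

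The diary conflict adds to this. Section 8.1.2 wants a single status epilepticus episode entered in the seizure diary as well as the AE log, and section 5.7 checks compliance against diary records. Taper medication is reconciled at Visit 17, yet no diary is dispensed to cover the taper.

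**Working it through.** **Inputs.** Visit 16 on Day 1085 and Visit 17 on Day 1099, ±4 days (Table 7). Taper length T of 0, 4 or 8 days after completion (Tables 5 and 6). Observation to 15 days after last dose (8.4).

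**The plan's own figure.** 1085 + 14 = 1099, so Visit 17 reproduces as two weeks after Visit 16.

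**Formulas.** Last dose L = 1085 + T. Off-drug days at Visit 17 = 1099 − L. The 15-day point = L + 15. Shortfall = (L + 15) − 1099.

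| Final dose (mg/kg/day) | T | Last dose | Off-drug days at Visit 17 (±4) | 15-day point | Shortfall |
|---|---|---|---|---|---|
| 0.2 | 0 | 1085 | 14 (10 to 18) | 1100 | 1 |
| 0.4 | 4 | 1089 | 10 (6 to 14) | 1104 | 5 |
| 0.5 with STP; 0.6 or 0.8 without | 8 | 1093 | 6 (2 to 10) | 1108 | 9 |

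If taper Day 1 is Day 1085 itself, the 8-day taper ends on Day 1092, giving 7 off-drug days and a shortfall of 8.

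**Early termination on day D.** Visit 17 is D + 14, the last dose of an 8-day taper is D + 8, and the 15-day point is D + 23. The shortfall is again 23 − 14 = 9 days.

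**TEAE window.** With the OLE Treatment Period ending at Visit 16, the Post-dosing Period closes on 1085 + 14 = Day 1099. After an 8-day taper, an event starting on Days 1100 to 1108 is inside the 8.4 observation period and outside the TEAE definition.

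**Diary, side by side.**
- Tables 1 and 2, Visit 16: collect and review, no dispense.
- Section 6.1.5, Visit 16: collect and review, no dispense.
- Tables 1 and 2, Visit 17: collect and review.
- Section 6.2, Visit 17: diary not listed.

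Visit 17 is thus to collect a diary that no earlier step hands out.

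**The case against.** The strongest reply is that the reporting duty does not depend on Visit 17. Section 8.4 holds it open to at least 15 days after the last dose. Ongoing AEs are followed to resolution or stabilization (4.4, 8.5.1), and information after discontinuation is collected where possible (4.4). This stands. A reader might infer that subjects tapering from the highest doses receive only 6 of the 15 days of AE follow-up; the documents do not support that. What is short is the last scheduled general AE contact and the TEAE window.

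A reader might also infer that seizures during the taper go unrecorded for want of a diary. That is too strong. Tables 1 and 2 expect a diary at Visit 17, so the passages contradict each other. Seizure worsening and status epilepticus are also reportable as AEs (8.1.1, 8.1.2), and AEs are recorded at Visit 17. The key effectiveness analysis does not use post-treatment diary counts.

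A third tempting reading takes the synopsis wording of up to two weeks as a 14-day taper, leaving no off-drug days at Visit 17. No row in Table 5 or 6 gives a dose beyond Day 8; every Step 3 cell in Table 6 is marked not applicable. The synopsis wording is an upper bound. The three-step description in 5.4.2.2 is a separate inconsistency.

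Sections 7.3.11 and 8.5.1 have staff ask about AEs at each site visit or clinical evaluation, which could be read as covering Visits 18 and 19. That conflicts with the cardiac-only footnotes. Even if it prevailed, the question would come about three months later, and the TEAE cut-off would still exclude the events.

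Finally, all subjects form one treatment group (10.3), so the dose-related difference biases no planned between-group comparison. Section 4.4 also allows immediate stopping, so a high final dose does not always mean an 8-day taper.

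**Conclusion.** The point holds as a timing mismatch. The last scheduled general AE contact and the TEAE cut-off fall about 14, 10 or 6 days after the last dose, which is 1, 5 or 9 days short of section 8.4. Non-cardiac events in the gap are reportable, but no scheduled visit solicits them and they are not counted as TEAEs. The diary entries for Visits 16 and 17 contradict each other.

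This rests on nominal visit days, the tabulated tapers, and the OLE Treatment Period ending at Visit 16. Section 5.4.2 supports the last assumption by placing the taper after completion of that period.

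Only subjects who stop ZX008 without moving to Study 1900 or commercial drug are affected. Their number is not given and may be small, but they include those who stop for an AE or worsening seizures. It is worth correcting because it decides which withdrawal events enter the main safety tables.

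**What to change.** 1. In 10.4 and 10.5.1, end the Post-dosing Period and the TEAE window 15 days after the last dose, including taper doses, to match 8.4. This is wording only.
2. Obtain general AEs through that day, in one of two ways:
   - Time Visit 17 from the last dose in 3.3, 6.2 and Tables 1, 2 and 7. No visit is added, but after an 8-day taper the interval without contact grows from 14 days to 1108 − 1085 = 23 days, spanning the taper.
   - Keep Visit 17 where it is and add a brief telephone AE check at last dose + 15 days. The cost is one call, and the existing contact is not delayed.
3. For subjects who taper, add diary dispensing at Visit 16 (6.1.5, Tables 1 and 2), and add diary collection and review to 6.2. The family keeps the diary until Visit 17.
4. Reconcile the taper length in the synopsis, the three-step wording in 5.4.2.2 and Table 6, where no dose goes beyond Day 8. No dose or taper step is proposed here.

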### 6.3 CARDIAC FOLLOW-UP VISIT (CLINIC VISIT 18, 19; 3 AND 6 MONTHS) AFTER LAST DOSE OF IMP

If the subject completes the study or discontinues from the study early, the subject will return to the clinic for follow-up cardiac testing (ECHO, ECG, and in some cases, physical examination). The timing and frequency of exams are in Table 8. As the ECHO and ECG will be administered in a separate clinic than the pediatric neurology clinic, an asymptomatic subject receiving a second follow-up ECHO and ECG does not require a physical examination. Cardiac follow-up visits are not required for subjects who have entered another ZX008 extension study or have transitioned to commercial drug.

Subjects with positive findings on ECHO, ECG and/or physical examination should continue to be followed until the finding is resolved or stable and unlikely to change.

If the subject is switching to commercially available drug, (subjects must have an ECHO within 3-6 months before starting commercial drug) the subject will complete the EOS visit and follow the drug administration process outlined for commercial product as advised by the subject’s physician. The post dosing and cardiac follow-up visits are not required.

**Table 8. Schedule of Post-Treatment Cardiac Follow-up**

Parameter	Duration of Fenfluramine Treatment				Have had any cardiac sign or symptom regardless of the time on study drug a
	Less than 2 weeks Cumulative	2 to 4 weeks	> 4 and < 13 weeks	> 13 weeks	
ECHO	No	Yes, 3 months post-treatment	Yes, 3 months post-treatment	Yes, 3 and 6 months post-treatment	Yes, 3 and 6 months post-treatment, and until resolved, or stable and unlikely to change
ECG	No	Yes, 3 months post-treatment	Yes, 3 months post-treatment	Yes, 3 and 6 months post-treatment	Yes, 3 and 6 months post-treatment and until resolved, or stable and unlikely to change
Physical examination	No	Yes, 3 months post-treatment	Yes, 3 months post-treatment	Yes, 3 months post-treatment only	Yes, 3 and 6 months post-treatment, and until resolved, or stable and unlikely to change

a Positive sign or symptom includes any development of valve thickening or regurgitation (“trace” or greater in mitral, aortic; mild or greater in pulmonary, tricuspid), or sign or symptom indicative of potential pulmonary hypertension as adjudicated by the IPCAB.

#### 6.4 ESTIMATED BLOOD VOLUME COLLECTION

The maximum total blood volume collected during the study for clinical laboratory testing, genotyping, and PK will be approximately 240.0 mL, as outlined in [Table 9](#).

**Table 9. Estimated Blood Volume Collectiona**

Assessment/ (Study Day)	OLE Treatment Period (study day)		
	15	30, 60, 90, 180, 270, 365, 455, 545, 635, 725, 815, 905, 995, 1085	Total
Clinical chemistry	--	7.5 mL at each visit	105 mL
LH, FSH, estradiol, testosterone, GH, prolactin	--	Included in Chemistry	
Hematology	--	2 mL at each visit	28 mL
IGF-1	--	3.5 mL at each visit	49 mL
Cannabidiol	--	2 mL at each visit	28 mL
AED plasma sample	1 x 2 mL	1 x 2 mL at each visit	30 mL
Approximate total blood volume per subject	2.0 mL	17.0 mL at each visit	240.0 mL

FSH=follicle stimulating hormone; GH=growth hormone; IGF-1=insulin-like growth factor 1; LH-luteinizing hormone

aIn concordance with The Seattle Children's Research Foundation Guidance ([Appendix 9](#)), blood collection volumes for children weighing up to 15 kg will be:

- The maximum allowable volume of blood in one draw is 22-30 mL (2.5% of total blood volume)
- The maximum in a 30-day period is 44-60 mL

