### 6.1.1 Screening Visit for de novo Subjects

For de novo subjects a screening period up to 28 days is required to determine eligibility prior to dosing. Clinical laboratory results and all ECHO/ECG results must be available and meet eligibility criteria prior to receiving the first dose of study medication at Visit 1. The following procedures will be performed during this screening period for all de novo subjects before the first dose of study medication:

- Obtain written informed consent for the study
- Obtain written informed consent from parent/caregiver to collect PedsQL Family Impact, HADS, and EQ-5D-5L ratings of parent/caregiver symptoms and quality of life
- Review inclusion and exclusion criteria
- Record demographic information
- Record medical, neurological, and epilepsy history
- Record current epilepsy status (number/type/duration seizures per month)
- Collect past 3 months (or available duration) of parent/caregiver seizure diary data if available (screen shots of cell phones are acceptable, as are photocopies of paper diaries or print outs) and place in source file
- Record prior medications
- Complete physical examination, including height, weight, and calculation of BMI
- Complete neurological examination
- 12-lead electrocardiogram
- Doppler ECHO (this must be obtained and results provided prior to starting ZX008)
- Vital signs
- Urine pregnancy test for females of child-bearing potential
- Laboratory evaluation (serum chemistry, hematology, urinalysis, etc)
- Urine THC panel
- Whole blood CBD
- Obtain blood sample for epilepsy genotype panel
- C-SSRS Baseline/Screening Assessment ([Appendix 2](#))
- CGI-I (assessed by parent/caregiver)
- CGI-I (assessed by investigator)
- BRIEF ([Appendix 3](#))
- QOLCE ([Appendix 4](#))
- Parent/Caregiver QoL using the EQ-5D-5L scale ([Appendix 7](#))
- Affective symptoms of parent/caregiver using the HADS scale ([Appendix 8](#))
- Instruct parent/caregiver on use of diary

- Dispense diary (after above procedures have been concluded)
- Record AEs

Review inclusion/exclusion criteria, including echocardiogram, ECG, clinical laboratory results, and approval from the Epilepsy Study Consortium. Only eligible subjects as specified by the inclusion and exclusion criteria with an independently confirmed diagnosis of DS by the Epilepsy Study Consortium, and approved by the sponsor, will be enrolled into the study and receive study medication.

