14.9 APPENDIX 9 – MAXIMUM ALLOWABLE BLOOD DRAW VOLUMES

Maximum allowable blood draw volumes:

PATIENT'S WEIGHT		TOTAL VOLUME	MAXIMUM mL IN ONE BLOOD DRAW	MAXIMUM mL IN A 30-DAY PERIOD
Kg	lbs	mL	2.5% of total blood vol	5% of total blood vol
1	2.2	100	2.5	5
2	4.4	200	5	10
3	6.6	240	6	12
4	8.8	320	8	16
5	11	400	10	20
6	13.2	480	12	24
7	15.4	560	14	28
8	17.6	640	16	32
9	19.8	720	18	36
10	22	800	20	40
11 thru 15	24 thru 33	880-1200	22-30	44-60
16 thru 20	35 thru 44	1280-1600	32-40	64-80
21 thru 25	46 thru 55	1680-2000	42-50	84-100
26 thru 30	57 thru 66	2080-2400	52-60	104-120
31 thru 35	68 thru 77	2480-2800	62-70	124-140
36 thru 40	79 thru 88	2880-3200	72-80	144-160
41 thru 45	90 thru 99	3280-3600	82-90	164-180
46 thru 50	101 thru 110	3680-4000	92-100	184-200
51 thru 55	112 thru 121	4080-4400	102-110	204-220
56 thru 60	123 thru 132	4480-4800	112-120	224-240
61 thru 65	134 thru 143	4880-5200	122-130	244-260
66 thru 70	145 thru 154	5280-5600	132-140	264-280
71 thru 75	156 thru 165	5680-6000	142-150	284-300
76 thru 80	167 thru 176	6080-6400	152-160	304-360
81 thru 85	178 thru 187	6480-6800	162-170	324-340
86 thru 90	189 thru 198	6880-7200	172-180	344-360
91 thru 95	200 thru 209	7280-7600	182-190	364-380
96 thru 100	211 thru 220	7680-8000	192-200	384-400

Based on blood volume of:

- 1 to 2 kg      100 mL/kg      (pre-term infant)
- >2 kg      80 mL/kg      (term infant - adult)

This information is similar to that used by the Committee on Clinical Investigations at Children's Hospital in Los Angeles, and at Baylor College of Medicine in Dallas, TX.

Adapted by [redacted] August 2001  
 Children's Hospital and Regional Medical Center Laboratory  
 Seattle, WA

Maximum allowable blood draw volumes:

[figure not shown]
PATIENT'S WEIGHT		TOTAL VOLUME	MAXIMUM mL IN ONE BLOOD DRAW	MAXIMUM mL IN A 30-DAY PERIOD
Kg	lbs	mL	2.5% of total blood vol	5% of total blood vol
1	2.2	100	2.5	5
2	4.4	200	5	10
3	6.6	240	6	12
4	8.8	320	8	16
5	11	400	10	20
6	13.2	480	12	24
7	15.4	560	14	28
8	17.6	640	16	32
9	19.8	720	18	36
10	22	800	20	40
11 thru 15	24 thru 33	880-1200	22-30	44-60
16 thru 20	35 thru 44	1280-1600	32-40	64-80
21 thru 25	46 thru 55	1680-2000	42-50	84-100
26 thru 30	57 thru 66	2080-2400	52-60	104-120
31 thru 35	68 thru 77	2480-2800	62-70	124-140
36 thru 40	79 thru 88	2880-3200	72-80	144-160
41 thru 45	90 thru 99	3280-3600	82-90	164-180
46 thru 50	101 thru 110	3680-4000	92-100	184-200
51 thru 55	112 thru 121	4080-4400	102-110	204-220

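### Table 9 footnote a applies Appendix 9's 11-15 kg blood limits to every child up to 15 kg, and the 240 mL maximum leaves no room for the de novo screening and genotyping draws

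*Protocol*

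**What the plan says.** Section 6.4 of the protocol states: "The maximum total blood volume collected during the study for clinical laboratory testing, genotyping, and PK will be approximately 240.0 mL", and points to Table 9 for the breakdown. Table 9 has one column for Day 15 and one for the 14 visits on Days "30, 60, 90, 180, 270, 365, 455, 545, 635, 725, 815, 905, 995, 1085". It has rows for chemistry, hematology, IGF-1, cannabidiol and the AED plasma sample. It has no genotyping row and no screening column.

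Footnote a to Table 9 says it agrees with Appendix 9, whose heading is "MAXIMUM ALLOWABLE BLOOD DRAW VOLUMES". It introduces its limits with "blood collection volumes for children weighing up to 15 kg will be", and then gives the single-draw limit: "The maximum allowable volume of blood in one draw is 22-30 mL (2.5% of total blood volume"). The 30-day limit that follows is 44-60 mL. No lower weight bound is given.

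Appendix 9 lists limits by weight, at 80 mL of blood per kg above 2 kg. The pair 22-30 mL and 44-60 mL stands in the row for 11 through 15 kg. Weights from 1 to 10 kg each have their own lower limits.

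Section 6.1.1 requires serum chemistry, hematology and whole blood CBD at screening of de novo subjects, and also: "Obtain blood sample for epilepsy genotype panel". Section 1.10 relies on 240 mL in its risk-benefit statement and excludes only repeat tests and additional tests ordered by the investigator.

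**The concern.** There are two separate points, and they concern different subjects.

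The first concerns the smallest children. The footnote is the place where a site looking at the blood-volume table finds its ceiling. For a child under 11 kg that ceiling is higher than the one in the appendix it cites. The inclusion criteria set a lower age of 2 years and no minimum weight, and Section 1.3 lists decreased weight and appetite among the most common adverse events. A site that checks a draw, or a repeat draw, against the footnote could pass a volume above the 2.5% and 5% limits that the protocol adopts.

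The second concerns de novo subjects, who are over 18 and up to 35 years old. A stated maximum should cover the subject with the most draws. Section 6.4 names genotyping as included and Section 6.1.1 requires it, yet the table behind the total does not count it. It does not count the screening laboratory draws either. Section 1.10 then uses the same total.

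**Working it through.** **Reproducing 240 mL.** Inputs from Table 9, per visit: chemistry "7.5 mL at each visit", hematology 2 mL, IGF-1 "3.5 mL at each visit", cannabidiol 2 mL, AED plasma sample 2 mL. Day 15 has one AED sample of 2 mL.

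- Per visit: 7.5 + 2 + 3.5 + 2 + 2 = 17 mL.
- Total: 2 + 14 × 17 = 240 mL.
- By row: 105 + 28 + 49 + 28 + 30 = 240 mL.

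The table's arithmetic is right. It also leaves 0 mL for anything before Day 15.

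**Appendix 9 limits by weight.** With 80 mL/kg, one draw is 2.5% × 80 × W = 2W mL, and 30 days is 5% × 80 × W = 4W mL. This reproduces the appendix rows used here.

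| Weight | Appendix 9, one draw / 30 days | Footnote's lowest values | Excess | 22 mL as % of blood volume |
|---|---|---|---|---|
| 11 kg | 22 / 44 mL | 22 / 44 mL | none | 2.50% |
| 10 kg | 20 / 40 mL | 22 / 44 mL | 10% | 2.75% |
| 9 kg | 18 / 36 mL | 22 / 44 mL | 22% | 3.06% |
| 8 kg | 16 / 32 mL | 22 / 44 mL | 38% | 3.44% |

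So the footnote departs from its source only below 11 kg.

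**The planned draw against the limit.** 17 mL ≤ 2W needs W ≥ 8.5 kg. The Day 30 and Day 60 visits each have a ±4-day window (Table 7), so they can fall 22 days apart (Day 34 to Day 56). Two visits then give 34 mL in 30 days, and 34 ≤ 4W again needs W ≥ 8.5 kg. From 8.5 kg upward the planned schedule respects Appendix 9. Only the ceiling quoted for children under 11 kg is wrong.

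**De novo total.** Screening is priced at Table 9 volumes, which is an assumption because Section 6.1.1 gives none. IGF-1 is not named in that section's laboratory item, which ends in an open-ended etc., so both readings are shown.

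- Without IGF-1: 7.5 + 2 + 2 = 11.5 mL; 240 + 11.5 = 251.5 mL (+4.8%).
- With IGF-1: 11.5 + 3.5 = 15 mL; 240 + 15 = 255 mL (+6.25%).
- The genotype sample comes on top. Its volume is not stated. If it were 2 to 10 mL, the total would run from 251.5 + 2 = 253.5 mL to 255 + 10 = 265 mL.

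Core-study subjects normally reuse core-study laboratory data at Visit 1 (footnotes to Tables 1 and 2), so this addition does not apply to them.

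**The case against.** The best defence is that little follows in practice. The footnote states a ceiling, not a volume to draw. It cites Appendix 9 and repeats the 2.5% basis, and the full weight table is in the same protocol. At 9 and 10 kg no planned draw breaches anything. The documents give no weights, so they do not show that any enrolled child is under 11 kg, let alone under 8.5 kg. All of this stands and limits the size of the point. It does not make the footnote agree with its source: 22 mL is not 2.5% of blood volume at 10 kg or below, and the 30-day line carries no percentage to correct it.

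A reader might infer that the schedule itself takes too much blood from small children. The documents do not support that from 8.5 kg upward. A breach at 10 kg can be constructed: two visits close together plus a chemistry repeat give 34 + 7.5 = 41.5 mL against 40 mL. But that needs shifted visit windows, a clinically significant abnormal result and a repeat within the same 30 days. It shows where the ceiling would come into play, not what is expected.

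On the total, it is fair to say that 240 mL is labelled approximate and that Section 6.4 names genotyping but not screening. Screening is covered only by implication, as laboratory testing during the study. A reader might also infer that the risk statement in Section 1.10 fails. It does not: at 46-50 kg, for example, Appendix 9 allows 92-100 mL in one draw, and an extra 11.5-15 mL plus one sample in an adult is small. Still, the shortfall is a missing category of draws rather than rounding, and these required draws are not among the exclusions in Section 1.10.

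**Conclusion.** Both points hold, each within a narrow scope.

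- **Footnote a** overstates the Appendix 9 limits for children under 11 kg, by at least 10% at 10 kg, 22% at 9 kg and 38% at 8 kg. This rests on Appendix 9's own rows and its 80 mL/kg basis. How many children are affected is unknown. From 8.5 kg the planned draws stay within the limits, so the wrong ceiling matters mainly when repeats are added. Below 8.5 kg the planned 17 mL itself exceeds 2.5%.
- **The 240 mL maximum** is correct for the draws in Table 9 but too low for de novo subjects: about 251.5-255 mL plus a genotype sample of unstated volume. This assumes Table 9 tube volumes at screening.

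Neither point shows that any subject was or will be over-drawn. A quoted safety threshold and a stated maximum nevertheless disagree with other parts of the same protocol, and they should be corrected.

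**What to change.** 1. Reconcile footnote a with Appendix 9, for example by referring to Appendix 9 at the subject's current weight (2.5% per draw, 5% per 30 days) instead of quoting one row for all children up to 15 kg.
2. Add the de novo screening draws and the genotype sample, with its volume, to Table 9. State whether IGF-1 is part of the screening panel.
3. Restate the maximum for de novo subjects in Sections 6.4 and 1.10.

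The cost is a wording and table correction. No visit, test or analysis has to change, and the only missing input is the genotype sample volume.
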